plus, 2) PRP or 3) PBMT and PRP on the management of knee OA by using molecular medicine techniques to examine orthobiologics (synovial and serum inflammatory biomarkers) during the management process.

9.3 Objectives/Specific Aims/Research Questions:

Describe the purpose and objective(s) of the study, specific aims, and/or research questions /hypotheses

Aim 1: Use molecular medicine techniques to assess the effect of PBMT on intra-articular administered PRP for the treatment of knee osteoarthritis via evaluation of synovial and serum inflammatory and reparative biomarkers.

Aim 2: Use molecular medicine techniques to compare the results of Standard Care vs PRP vs PRP + PBMT in the treatment of knee osteoarthritis - using synovial and serum inflammatory and reparative biomarkers.

Aim 3: Analyze the relationship between self-reported pain and functionality and treatment mechanism (SOC, PRP or PRP +PBMT).

Aim 4: Analyze the intersectionality between participant self-reported pain and functionality and precision medicine markers across treatment groups (SOC, PRP, and PRP + PBMT)

9.4 Study Design:

Describe study design in one to two sentences (e.g., prospective, use of existing records/data /specimens, observational, cross-sectional, interventional, randomized, placebo-controlled, cohort, etc.). Specify the phase – Phase I, II, III, or IV – for FDA-regulated investigational drug research

This discovery-based and randomized control trial concerning knee OA will investigate the effect of PBMT and intra-articular administered PRP treatment on clinical outcomes (e.g., pain scores) and biomolecular signatures (DNA, RNA, or protein levels) in the blood or synovial spaces. We will specifically be comparing treatments, (1) PT, (2) PT+PRP, (3) PT+PBMT, (4) PT+PRP+PBMT, with clinical outcomes and biomolecular signatures.

9.5 Target Population:

Describe the population to whom the study findings will be generalized

Active-duty service members (ADSMs) and civilian populations experiencing knee OA

9.6 Benefit to the DoD:

State how this study will impact or be of benefit to the Department of Defense

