Synovial fluid will be aspirated according to standard of care (SOC) guidelines. If, at the time of joint aspiration, there is a "dry tap" (i.e., no fluid is returned), the provider will lavage the joint with a standardized quantity (10ml) of sterile Normal Saline and then aspirate the lavage. There are no harmful effects from lavaging the synovial joint with sterile saline.

The synovial fluid will be labeled with a sample ID and study visit, and transported to MAMC Department of Clinic Investigation (DCI) for storage and processing. Any excess synovial fluid will be safely discarded per standard protocol. Ice will be utilized when necessary.

Synovial fluid processing and storage are outlined below in respective sections.

The research team will maintain a biospecimen sample master key that links the sample IDs to the participant study IDs. No PII/PHI will be stored with the biospecimen sample key.

Randomization:

Participants that meet final eligibility criteria will be randomized to a study arm using a computer-generated randomization model prepared by the study biostatistician, to assign participant 1:1:1:1 across all study arms (PT, PT+PRP, PT+PBMT, or PT+PRP+PBMT).

Study Intervention:

Study interventions will be documented in the participant's EMR and on the Study Treatment Documentation Log (Appendix F).

Standard of Care (SOC) Physical Therapy (PT):

All participants will complete a standard PT program addressing individual strength, mobility, and flexibility deficits in both proximal and distal muscle groups. The provider may also use other modalities to address distal issues. If a participant has not been placed on profile at the time of consent, a profile may be written by the study medical provider to ensure limitation of activities, as appropriate.

The PT treatment participants receive in this study will be standard of care; that is, the PT treatment regimen will not be standardized across study participants and/or dictated by study-specific criteria. PT treatments will be recorded on a Chart Review CRF (Appendix I).

SOC PT + Platelet-Rich Plasma (PRP):

In addition to SOC PT, participants assigned to PT+PRP group will receive PRP treatment, as outlined below.

PRP Preparation:

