- RNA - Data will be generated in fastq format (if performing sequencing, e.g., with a MiSeq, NextSeq, MinION) and summarized as counts at the isoform or gene level. To arrive at the count level, raw data will be processed by performing alignment, pseudo-alignment, or any other mapping technique. Different software may be used to do this, e.g. Sleuth. Statistical analyses will be performed using standard workflows, e.g. DESeq2, edgeR. We may also use RNA quantification methods such as the nCounter, PCR arrays, and qPCR. For the latter methods, we will use the manufacturer's software (e.g. nSolver), the delta delta Ct method, or standard curves for absolute quantification. We will use loading controls such as GAPDH, RPLP0, or similar when needed.
- Protein - We will perform ELISAs (generate spectrophotometric data), Western blots (generate densitometric data), use arrays or multi-plex or other intermediate throughput techniques (e.g., Olink, BioPlex), mass spectrometry data (outputs vary but will be summarized into counts or relative expression levels), or other relevant methodologies.

Sample processing is as follows:

- *Synovial Fluid:*
 - Synovial fluid (SF) will be collected in a 1.5 mL Eppendorf tube (ept).
 - SF sample will be transferred to the lab on ice.
 - SF sample will be centrifuged at 1500g for 15 min in a refrigerated centrifuge to clear SF from cellular debris.
 - Supernatant (synovial fluid) will be immediately transferred into a clean 1.5 mL ept.
 - Protease inhibitor will be added at 1X final concentration (100-fold dilution of the original 100X).
 - 200-500µL of SF will be aliquoted into a pre-labeled 1.5 mL tube and stored at -80° C.
- *Proteomics analysis:*
 - 4-5 mL of blood will be collected into a sodium heparin tube, and an additional 4-5 mL of blood will be collected into a K2 EDTA tube.
 - Blood samples will be transferred to the lab within 20 minutes of collection.
 - Blood samples will be centrifuged at 2000 g for 15 minutes using a refrigerated centrifuge.
 - The top liquid component (plasma) will be immediately transferred into a clean 15 mL polypropylene conical tube.
 - Protease inhibitor will be added at 1X final concentration (100-fold dilution of the original 100X).
 - 200-500 µL of plasma will be aliquoted into a pre-labeled 1.5 mL tube and stored at -80°C.
- *DNA/RNA analysis:*
 - 3ml of blood will be drawn into a DNA/RNA Shield Blood Collection Tube.
 - Blood samples will immediately be inverted 10 times (gently).

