 - Blood sample will be transported at 4°C to MAMC DCI.
 - Once at DCI, samples will be aliquoted into cryovials (200-500ul each) and stored at -80°C.
 - At a later date, when a complete batch of samples are available, samples meant for genomic or transcriptomic analyses will be thawed at 4°C or room temperature and their nucleic acids will be extracted using a kit appropriate for the sample and nucleic acid type (e.g., Zymobiomics Microbial DNA extraction kit or Qiagen DNA and RNA extraction kits).
 - Extracted DNA and RNA will be stored at -80°C for later processing.
 - DNA or RNA extracts will be barcoded using the appropriate protocol (e.g., for 16S or RNA sequencing on the Illumina MiSeq) and processed according to the manufacturer's protocols or as needed following experimental optimization.

Once sufficient sampling has been met, batch analyses will be completed for the respective biomarkers of interest. Single sample analysis may also occur for optimization and preliminary results.

These assays will evaluate many matrix and immune markers that may include ADAMTS-4 & 5, MMP 7 & 9, TGF-B, Aggrecan, HYAL2, CRP, HA, CD14, CD16, and CD64.

Additional Info - MIRROR/USU:

This research study is being conducted as part of Musculoskeletal Injury Rehabilitation Research for Operational Readiness (MIRROR), which is based out of the Department of Physical Medicine & Rehabilitation (PM&R) at the Uniformed Services University (USU).

MIRROR is focused on advancing musculoskeletal injury (MSI) rehabilitative care within the military healthcare system in order to reduce the burden MSIs have on military readiness and to ultimately enhance the operational capabilities of the armed forces. MSIs affect approximately 800,000 service members annually and result in 25 million days of limited duty. These conditions are the primary reasons for medical discharge/downgrade and result in 34% of medical evacuations from theatre. MIRROR was developed as a means to study risk factors of common MSIs, generate prevention strategies, optimize treatments, and establish return-to-duty criteria that is based on scientific evidence rather than case-specific clinical judgment alone.

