11.5 Please provide a justification for your sample size

Since this is a discovery-based study of a novel topic, limited data are available with which to perform a power analysis. Thus we used a G*Power for a general comparison analysis without needing to root firmly in one specific variable.

If we are able to enroll 150 participants (a minimum of 92 post-attrition), assuming an effect size of .2, we will achieve 90% power. Effect size assumptions were taken from Tomazoni et al. 2016 based on the comparison of control versus PBMT with regards to biomarkers of gene expression that we assume to be an acceptable proxy for our primary comparison with regards to our biomarkers of concern. Significance threshold for power calculations was considered to be .01 to account for false discovery rate within our set of primary biomarker outcomes. Power calculations were performed using the WebPower package and the R Programming language.

11.6 Data Analysis Plan: Complete description: Background, Objectives, Design, Step by Step how the project is going to be done, Data analysis plan:

Aim 1 will be evaluated by comparing the PRP only and the PRP + PBMT treatment arms at six weeks relative to baseline. Generalized additive models predicting the fractional change in outcome measure at 6 weeks will be used.

Aim 2 will compare across all four treatment arms and will use Multi-Level models comparing the three treatment arms across time points and including random effects.

Aim 1 will include biomarker measures only; Secondary Aim 2 will include both biomarker measures and self-reports.

Hypothesis tests will be two-tailed and statistical significance will be considered at the putative threshold ($\alpha=0.05$). Any secondary P-values will be subject to a false discovery rate adjustment in keeping with best statistical practices. Multilevel models will incorporate random effects to account for repeated measures, using distribution families and link functions appropriate for the outcomes of interest, determined using QQ plots analyzed for best model fit. All statistical analyses will be performed using the R Programming language.

Clinical outcomes (pain scores) will be evaluated via ANOVA and post-hoc tests (Tukey's HSD test). A non-parametric alternative will be used if assumptions are not met.

Molecular Analyses:

DNA/RNA Analyses

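### Dry-tap saline lavage samples have no described flag, returned volume or dilution correction, so pooling them with neat fluid can cost power and, if dry-tap rates differ by arm, bias change in synovial protein

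*Combined protocol and SAP*

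**What the plan says.** All references are to the combined protocol and SAP.

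- **Collection (10.1, Synovial Fluid Collection).** When no fluid returns, "the provider will lavage the joint with a standardized quantity (10ml) of sterile Normal Saline and then aspirate the lavage". On labelling: "The synovial fluid will be labeled with a sample ID and study visit". On the remainder: "Any excess synovial fluid will be safely discarded per standard protocol".
- **Processing (10.1, Specimen Processing).** One synovial pathway is described: "Synovial fluid (SF) will be collected in a 1.5 mL Eppendorf tube (ept"), then centrifugation, transfer, protease inhibitor, aliquots and freezing. No step separates lavage from neat fluid or normalises for dilution. A normaliser is named only under RNA: "We will use loading controls such as GAPDH, RPLP0, or similar when needed".
- **Assay timing (10.1).** "Once sufficient sampling has been met, batch analyses will be completed for the respective biomarkers of interest".
- **Aims (9.3).** Aim 1 works "via evaluation of synovial and serum inflammatory and reparative biomarkers", and synovial fluid is a listed substrate for protein measurement.
- **Analysis (11.6).** Aim 1 compares PRP with PRP plus PBMT at six weeks relative to baseline: "Generalized additive models predicting the fractional change in outcome measure at 6 weeks will be used". Aim 2 extends to all arms.
- **General rules (11.1).** Confounders are to be modelled where possible. Outliers may be removed, replaced or kept. Lavage is not mentioned.

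**The concern.** A lavage aspirate and a neat aspirate are not on the same concentration scale. The saline volume is fixed, but the fluid already in the joint is unknown, so the dilution is unknown and differs between people and visits. Fractional change divides one visit by the other. A pair with one neat and one lavage sample therefore carries the whole dilution factor as apparent biological change.

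Two harms can follow for protein in synovial supernatant.

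- **Lost power.** Discordant pairs add large noise, so a real change may be missed.
- **Bias.** If dry taps at six weeks are more frequent in one arm, that arm shows falsely lower synovial protein across all soluble markers. More participants would not cure this.

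Bias is possible in both aims. Section 9.2 suggests that PRP and PBMT together may reduce inflammation more. If dry taps become commoner as effusion falls (an assumption), the 6-week rate could differ even between the two Aim 1 arms. For Aim 2 there is a second possible route: the PRP arms' aspiration is described as part of an ultrasound-guided procedure, whereas the general collection text refers only to standard-of-care aspiration.

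Part of the information cannot be recovered later. A 10 mL lavage goes into a 1.5 mL tube and the excess is discarded, so the returned volume is lost unless it is written down at collection.

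**Working it through.** **The plan's own figures.** The documents give no dry-tap rate, residual volume or marker variance, so there is no stated figure on this point to reproduce. The general power claim in 11.5 (90%, N = 92, effect size 0.2, alpha .01) is matched by a noncentral F test with f-squared = 0.2 and 2 numerator df (0.901). It makes no allowance for dilution. The 31 per arm used below follows the 30-31 in 11.2; 92 over four arms is 23.

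**Step 1: dilution.** Lavage volume is 10 mL (10.1). Residual volume V is assumed to be 1, 2 or 5 mL. D = (10 + V)/V.

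| V (mL) | D | Neat then lavage, 1/D - 1 | Lavage then neat, D - 1 |
|---|---|---|---|
| 1 | 11 | -91% | +1000% |
| 2 | 6 | -83% | +500% |
| 5 | 3 | -67% | +200% |

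Both right-hand columns assume no biological change.

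**Step 2: added variance, equal dry-tap rates.** Assume a marker CV of 50% and a between-visit correlation of .5. Then s² = ln(1.25) = 0.223 and Var(log change) = 2 × 0.223 × (1 - .5) = 0.223 (SD 0.47). With independent dry taps at rate p per visit, the share of discordant pairs is d = 2p(1 - p): 0.095 at 5% and 0.32 at 20%. Relative effective sample size on the log scale is 0.223/(0.223 + d × ln(D)²).

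- 5%, V = 1: 0.223/(0.223 + 0.095 × 5.75) = 0.29. V = 5: 0.223/(0.223 + 0.095 × 1.207) = 0.66.
- 20%, V = 1: 0.223/(0.223 + 0.32 × 5.75) = 0.11. V = 5: 0.223/(0.223 + 0.32 × 1.207) = 0.37.

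**Step 3: power by simulation.** Assume a true 30% reduction and two-sided .05. Results are for the Wilcoxon rank sum test; ranges are over V = 1 to 5 mL.

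| Dry taps per visit | 31 per arm | 23 per arm |
|---|---|---|
| None | about 81% | 68% |
| 5%, independent | 63-69% | about 48-55% |
| 20%, independent | 29-42% | 22-33% |
| 20%, highly persistent (latent r = .95) | 68-72% | 54-58% |

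In the persistent case at 31 per arm, power is 58% if V also varies between visits. A Welch t-test on raw fractional change does worse: from about 80% with no dry taps to 13-55% at 5% and 9-33% at 20%, independent.

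**Step 4: no true effect, 31 per arm.** Between-arm bias in log change is -(difference in 6-week dry-tap rate) × ln(D). Baseline rate is 20% in both arms.

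| 6-week rates | Bias in log change, V = 5 to 1 mL | Wilcoxon false positives |
|---|---|---|
| 20% vs 20% | 0 | about 5% |
| 20% vs 30% | -0.11 to -0.24 | about 8-9% |
| 20% vs 40% | -0.22 to -0.48 | about 17-20% |

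A bias of -0.22 to -0.48 is a false reduction of 20% to 38% (1 - e^-0.22 and 1 - e^-0.48).

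**The case against.** **The record may exist elsewhere.** Appendices D, H and S, the laboratory SOPs and the repository quality-control record were not available. A reader might infer that lavage status is not recorded at all. The documents do not support that; they support only that the supplied text does not describe it. The line in 10.1 on documenting synovial collection at baseline does not settle the matter either. This objection stands and limits the claim.

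**The size is assumed.** Dry-tap rate, V, variance, correlation and effect are all inputs chosen for illustration. Persistence alone moves Wilcoxon power at 20% dry taps from 29-42% to 68-72%. At alpha .01, the level used in 11.5, clean power is already about 60%. This also stands.

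**The general safeguards might suffice.** They do not replace a flag. Adjusting for a confounder (11.1, 11.6) works only if lavage is recorded. The Wilcoxon fallback limits the loss without removing it, and 11.1 attaches it to the t-test, not to the Aim 1 additive model. A reader might go further and infer that the outlier rules would delete only one direction of discordant pair. The plan fixes no numerical rule, so that does not follow. What can be said is that nothing in the outlier wording identifies lavage pairs.

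**Both Aim 1 arms receive PRP, so equal rates may seem likely and power the main loss.** The arms differ by PBMT, and the plan's own rationale expects the combination to be more anti-inflammatory. No document gives rates by arm, so equal and unequal rates are equally unsupported.

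**Conclusion.** The concern holds in a limited form. As written, the supplied text leads to lavage samples, diluted 3- to 11-fold for V of 5 to 1 mL, being pooled unmarked with neat fluid and analysed as fractional change. That can reduce power for synovial supernatant protein. It can also bias the contrast, in Aim 1 or Aim 2, if 6-week dry-tap rates differ by arm.

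The sizes shown above are conditional on assumed inputs, and losses are smaller if the same knees are dry at both visits. Two stronger readings are tempting: that the harm is mainly lost power, and that the result will favour the combination arm. The first needs equal 6-week dry-tap rates and the second needs a higher rate in that arm; the documents show neither.

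The scope is narrow: plasma and blood RNA markers are unaffected. The change should be made, with medium confidence because the appendices and SOPs could not be read.

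**What to change.** 1. At baseline and six weeks, record neat or lavage and the volume returned, before excess fluid is discarded. If an appendix or SOP already does this, cite it in 10.1 and 11.6.
2. Prespecify a dilution normalisation for synovial protein, with the marker chosen by the laboratory and checked in neat samples. Options include a ratio to plasma from the same visit, or total protein with the caveat that treatment may change it. Analyse log change of the corrected values.
3. Report the dry-tap rate by arm and visit.
4. Add a sensitivity analysis in both-neat pairs, stating that 6-week lavage status arises after randomisation, and give the pairs lost per arm. If no normaliser can be verified, do not pool uncorrected lavage with neat samples; report the both-neat result with that caveat.
5. Fix these choices before biomarker data are joined to treatment codes.

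**Cost.** Two form fields per visit, one assay on samples already stored for batch analysis, and SAP wording. Assay price and sample volume needed are not in the documents.

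The normaliser adds noise. An assumed error CV e on every sample adds 2 ln(1 + e²) to the variance. At 10% to 20% this leaves 92% to 74% of the effective sample size and Wilcoxon power of 78% to 68%, if treatment does not affect the normaliser.

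Both-neat pairs keep 0.95² = 90% of pairs and 77% power at 5% independent dry taps, or 0.80² = 64% of pairs and 60% power at 20%. Those powers assume dryness is unrelated to marker level or treatment. With persistent dryness and stable V, neither step gains much power; the record by arm would still show whether bias is a risk.
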